## 8. Drug Formulation and Procurement

Both temozolomide and capecitabine will be obtained commercially.

### 8.1 Temozolomide

#### 8.1.1 Other Names

Temodar

#### 8.1.2 Classification

Cytotoxic chemotherapy, alkylating agent

#### 8.1.3 Mode of Action

Temozolomide [8-carbamoyl-3-methylimidazo(5,1-d)-1,2,3,5-tetrazin-4(3H)-one] (Temodal) is an imidazole tetrazinone compound developed by Schering-Plough for use as an antineoplastic agent. TMZ is a prodrug that spontaneously hydrolyzes to 5-(3-methyltriazen-1-yl)imidazole-4-carboxamide (MTIC), which is also the active metabolite of dacarbazine. Dacarbazine, however, requires hepatic metabolism for formation of this metabolite, which results in variable levels. TMZ is stable at an acidic pH, allowing oral absorption, and has a broad biodistribution.

Temozolomide is not directly active but undergoes rapid nonenzymatic conversion at physiologic pH to the reactive compound 5-(3-methyltriazen-1-yl)-imidazole-4-carboxamide (MTIC). The cytotoxicity of MTIC is thought to be primarily due to alkylation of DNA. Alkylation (methylation) occurs mainly at the O6 and N7 positions of guanine.

#### 8.1.4 Storage and Stability

As a solid, temozolomide is thermally stable and does not decompose when exposed to light. In solution, temozolomide undergoes rapid hydrolysis in a basic environment. The product label recommends storage at room temperature 25°C (77°F). Temozolomide should be stored at 20-25°C (68-77°F), excursions permitted between 15-30°C (59-86°F).

#### 8.1.5 Dose Specifics

ARM A: 200 mg/m^2 po QD on days 1-5

ARM B: 200 mg/m^2 po QD on days 10-14

The temozolomide dose will be capped at 400 mg daily and is available as 5, 20, 100, 140, 180, or 250 mg capsules. The calculated dose by body surface area (BSA) will be rounded down to minimize the number of pills required.

#### 8.1.6 Preparation

N/A

8.1.7 Route of Administration  
Oral

8.1.8 Incompatibilities  
N/A

8.1.9 Availability  
Commercial supply

8.1.10 Side Effects  
Hematologic: anemia, neutropenia, thrombocytopenia, aplastic anemia.  
Constitutional: fatigue, anorexia, weight loss  
Dermatologic: rash, pruritus, Stevens-Johnson-Syndrome  
Gastrointestinal: nausea, vomiting, constipation, diarrhea, abdominal pain, stomatitis, dysphagia  
Infections: PCP infection  
Metabolic: hyperglycemia, liver or kidney abnormalities  
Neurologic: headache, somnolence, insomnia, blurred vision  
Oncologic: secondary malignancy  
Psychiatric: anxiety, depression

8.1.11 Nursing/Patient Implications

- 8.1.11.1 Monitor CBC and platelet count prior to drug administration.
- 8.1.11.2 Symptom management of expected nausea, vomiting, photosensitivity, and mucositis within ≤ 3 months prior to treatment.
- 8.1.11.3 Ondansetron will be given as a premedication to prevent nausea 30-60 minutes prior to the temozolomide dose.
- 8.1.11.4 Temozolomide should be taken by mouth after fasting from solid food for two hours.
- 8.1.11.5 Temozolomide tablets must not be crushed and must be administered whole.
- 8.1.11.6 Temozolomide missed doses will not be made up, and patients should not double-up on missed doses during treatment. Do not repeat dose if vomiting occurs after dose is administered.
- 8.1.11.7 Liver function tests should be performed after each treatment cycle. For patients with significant liver function abnormalities the benefits and risks of continuing temozolomide should be carefully considered.

8.2 Capecitabine

8.2.1 Other Names  
Xeloda

8.2.2 Classification  
Cytotoxic chemotherapy, anti-metabolite

8.2.3 Mode of Action  
Capecitabine is a fluoropyrimidine carbamate that is an orally active prodrug of 5-fluorouracil. Normal cells, as well as tumor cells, metabolize 5- fluorouracil into 5-fluoro-2'deoxyuridinemonophosphate (FdUMP) and 5-fluorouridine triphosphate (FUTP). Both are metabolites that cause cell injury by two different mechanisms. FdUMP and the folate factor, N5-10-methylenetetrahydrofolate, bind to thymidylate synthase (TS) to inhibit the formation of thymidylate. This deficiency of thymidylate causes cell cycle division to halt. This is because thymidylate is necessary for thymidine triphosphate production, which is essential for DNA synthesis. FUTP works by incorporating itself into transcription in place of uridine triphosphate therefore interfering with RNA transcription and protein synthesis.

8.2.4 Storage and Stability  
Capecitabine is supplied as biconvex, oblong film-coated tablets, available as 500 mg tablets (peach). Capecitabine is stored at 25°C, with excursions permitted to 15 to 30 °C.

8.2.5 Dose Specifics  
ARM A: None  
ARM B: 750 mg/m^2 po BID on days 1-14  
The calculated total daily dose by body surface area (BSA) will be rounded down to the nearest 500 mg allow doses using 500 mg tablets.

8.2.6 Preparation  
N/A

8.2.7 Route of Administration  
*Oral*

8.2.8 Incompatibilities  
N/A

8.2.9 Availability  
Commercial supply

8.2.10 Side Effects

Hematologic: anemia, neutropenia, thrombocytopenia  
Cardiovascular: Edema, venous thrombosis  
Constitutional: fatigue, pyrexia, swelling in hands, feet or abdomen, pain, chest pain  
Dermatologic: hand-foot syndrome, dermatitis, skin discoloration, alopecia  
Gastrointestinal: diarrhea, nausea, vomiting, stomatitis, abdominal pain, gastrointestinal motility disorder, constipation, taste disturbance, upper GI inflammatory disorders, gastrointestinal hemorrhage, ileus  
Hepatic: hyperbilirubinemia  
Infections: bacterial or viral  
Metabolic: appetite decreased, dehydration  
Musculoskeletal: back pain, arthralgia  
Neurologic: peripheral sensory neuropathy, headache, dizziness, insomnia  
Ocular: eye irritation, vision abnormal  
Psychiatric: mood alteration, depression  
Pulmonary: dyspnea, cough, pharyngeal disorder, epistaxis, sore throat  
Vascular: venous thrombosis

8.2.11 Nursing/Patient Implications

- 8.2.11.1 Monitor CBC and platelet count prior to drug administration.
- 8.2.11.2 Administer doses at least 8 hours apart.
- 8.2.11.3 Symptom management of expected nausea, vomiting, diarrhea, and hand-foot skin syndrome.
- 8.2.11.4 Capecitabine tablets should be swallowed with water within 30 minutes after a meal.
- 8.2.11.5 Capecitabine tablets are allowed to be crushed.

## 9. Statistical Considerations

### 9.1 Expected Accrual Pattern

While neuroendocrine tumors (NETs) are relatively rare in the population, the absence of standard treatment options has led to significant interest and rapid accrual to clinical trials in this disease in recent years. For example, the recently completed industry-sponsored RADIANT3 study accrued 410 patients with pancreatic NETs over a period of 21 months from 18 countries (83 sites) for an overall accrual rate of 19 patients per month. CALGB 80701, a randomized study of everolimus with or without bevacizumab in patients with advanced pancreatic NET opened in October 2010 and has accrued over 70 patients, with a current accrual rate of approximately 6 per month. CALGB 80701 targets a similar population to the currently proposed study and will likely complete accrual within the next year. Assuming participation of several cooperative groups within the U.S., we similarly expect to enroll approximately 6 patients per month to this trial. Accrual is expected to be complete within 2 years from study activation.

### 9.2 Treatment Assignment

Patients will be randomized with equal probability to treatment with single agent temozolamide or the combination of temozolamide and capecitabine using a stratified permuted blocks algorithm with stratification based on prior treatment with everolimus (Yes vs No), prior treatment with sunitinib (Yes vs No) and concurrent administration of octreotide (Yes vs No).

### 9.3 Statistical Design and Efficacy Monitoring

The primary endpoint of this trial is progression-free survival (PFS). Patient assessments will be made every 3 months.

This study will require a minimum of 138 patients (or a maximum of 145 patients to allow for 5% ineligibility) to be accrued at the rate of roughly 6 patients per month. With 23 months of accrual time and 13 months of follow-up (3 years total study time), this trial will have at least 81% power to detect a difference in median PFS between the treatment arms of 9 versus 14 months (hazard ratio of 0.64) using a two-sided log-rank test at the overall 0.20 significance level. The assumption of 9 months for the temozolamide arm is based on historical data of temozolamide alone and temozolamide-based regimens as described in the introduction. The assumption of 14 months for the combination arm is based a goal of improving treatment by 55% (which conservatively approximates the Strosberg PFS data of 18 months).

There will be two log-rank tests conducted, an interim analysis at 76% information (at 80 PFS events, projected to occur just after the end of the accrual period at 26 months) and a final analysis at 100% information (105 PFS events), projected to occur at 3 years from the start of accrual. The overall type I error will be controlled using an O'Brien-Fleming boundary function. Using this boundary, if the repeated two-sided 95% confidence interval on the hazard ratio does not contain the target alternative hazard ratio of 0.64, consideration will be given to declaring the study negative and reporting the results. If the interim log-rank test is positive, the study can be reported early before the projected end of the follow-up period.

Response rate (RR) will be a secondary endpoint. RR will be defined by revised RECIST criteria version 1.1 and include complete responses and partial responses. Prior studies of single agent temozolomide suggest that the response rate associated with single-agent temozolomide is 8-24%; however, overall response rates associated with other temozolomide-based regimens in this disease are between 30-40%. For the purposes of this study, we assume that single agent temozolomide will be associated with a response rate of 33%. Retrospective series of temozolomide/capecitabine have reported response rates of 59-70% in advanced pancreatic neuroendocrine tumors.

With 138 patients there will be at least 80% power to detect an absolute difference of 20% in the objective response rates (for example, between 33% and 53% true response rates) using a two-group Fisher's exact test at an overall two-sided 20% significance level. In addition, within each arm, a 90% confidence interval on the true objective response rate will be no wider than 21 percentage points. Overall survival will also be a secondary endpoint but power for overall survival comparisons will be limited.

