#### 9.4 Safety Monitoring

Interim analyses of toxicity are performed twice yearly for all ECOG-ACRIN studies. Expedited reporting of certain adverse events is required through the CTEP-AERS system, which is monitored continuously with formal notifications monthly of unexpected grade 4 and 5 events. Formal comparison of toxicity rates between the arms is not a goal of this trial and the sample size will provide sufficient power for detecting only relative large difference in adverse events. With at least 69 patients per treatment arm, a 90% confidence interval on any adverse event rate will be no wider than 21 percentage points and there is at least 87% probability of observing one or more rare events (3% true probability) in either treatment arm.

Reports of these analyses are sent to the ECOG-ACRIN Principal Investigator or Senior Investigator at the participating institutions. Expedited reporting of certain adverse events is required, as described in Section [5](#).

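### Does the interim futility rule fail because it takes a 95% repeated interval from a boundary set at overall 0.20 and gives no direction?

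*Combined protocol and SAP*

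**What the plan says.** Section 9.3 (Statistical Design and Efficacy Monitoring) compares median PFS of 9 and 14 months, a hazard ratio of 0.64, "using a two-sided log-rank test at the overall 0.20 significance level". There are two looks, at 80 and 105 PFS events. The first is "projected to occur just after the end of the accrual period at 26 months". Of the two looks together it says: "The overall type I error will be controlled using an O'Brien-Fleming boundary function".

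The futility condition comes next: "Using this boundary, if the repeated two-sided 95% confidence interval on the hazard ratio does not contain the target alternative hazard ratio of 0.64". Its consequence is that "consideration will be given to declaring the study negative and reporting the results". The following sentence covers the opposite result: "If the interim log-rank test is positive, the study can be reported early before the projected end of the follow-up period".

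Elsewhere the plan uses interval levels that do not match its 20% test level. For response, "a 90% confidence interval on the true objective response rate will be no wider than 21 percentage points"; in Section 9.4, "a 90% confidence interval on any adverse event rate will be no wider than 21 percentage points".

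**The concern.** There are two apparent faults.

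**Level.** A repeated confidence interval takes its coverage from the boundary used to build it. The only overall level that Section 9.3 attaches to its boundary is two-sided 0.20, which gives an 80% repeated interval. A 95% repeated interval needs an O'Brien-Fleming boundary at overall two-sided 0.05, and none is written down. One analyst could follow the printed 95% and another the 0.20 boundary. Their futility cut-offs would differ, and they would disagree at an observed hazard ratio of 1.00, a result that a futility rule exists to handle.

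**Direction.** The condition is only that 0.64 lies outside the interval. An interval wholly below 0.64, showing a benefit larger than targeted, meets it literally. The rule would then point to a negative study while the efficacy test on the same data was positive.

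At stake are the chance of closing an ineffective comparison early, the chance of wrongly abandoning an effective one, and the clarity of a pre-specified rule on the primary endpoint.

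**Working it through.** **Inputs, all from Sections 9.2 and 9.3.** Equal allocation; 80 interim and 105 final events; target hazard ratio 9/14 = 0.643 (printed as 0.64); overall two-sided level 0.20; stated power at least 81%. The plan does not name the O'Brien-Fleming version, so three are used: classic; a spending function on the two-sided level; and a spending function on each tail. Ranges run across the three.

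**1. Stated power.** For a single look (Schoenfeld), power = Φ(√105/2 × |ln(9/14)| − 1.2816) = Φ(2.264 − 1.282) = 83.7%. With two looks (bivariate normal, information 80/105 = 0.762), power is 82.0–82.8%, or 81.1–81.8% with Freedman's drift. This agrees with the plan's figure. At a 0.05 level, single-look power would be 61.9%, so 0.20 is clearly the test level.

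**2. The two readings at 80 events.** SE(log HR) = 2/√80 = 0.2236. The repeated interval is log HR ± c × 0.2236, where c is the interim critical value. Its lower limit exceeds 0.64 when the observed HR exceeds 0.64 × exp(0.2236c). With the classic boundary:

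- 95%: 0.64 × exp(0.2236 × 2.311) = 1.073
- 80%: 0.64 × exp(0.2236 × 1.575) = 0.910

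| | 95% (overall 0.05) | 80% (overall 0.20) |
|---|---|---|
| Interim critical value | 2.25–2.32 | 1.47–1.58 |
| Futility signal above observed HR | 1.06–1.08 | 0.89–0.91 |
| Interval at observed HR 1.00 (classic) | 0.60–1.68, no signal | 0.70–1.42, signal |
| Signal probability, true HR 1 | 37–40% | 66–70% |
| False signal, true HR 0.64 | about 1% | about 6–7% |
| Power if every signal stops the trial, Schoenfeld | 82.0–82.8% | 81.5–82.4% |
| Same, Freedman | 81.1–81.8% | 80.5–81.4% |

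The 95% rule costs under 0.01 points of power against having no futility rule. The 80% rule costs about 0.4 to 0.5 points and can fall below the stated 81%.

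**3. The literal wrong-side trigger.** The classic 95% interval lies wholly below 0.64 when the observed HR is under 0.64 × exp(−0.2236 × 2.311) = 0.38. The efficacy boundary is already crossed at exp(−0.2236 × 1.575) = 0.70 (0.70–0.72 over the versions). Every result in this branch is therefore one that the next sentence of Section 9.3 treats as positive. Its probability at a true HR of 0.64 is about 1%.

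**4. Time at stake.** Assume exponential PFS, 138 patients accrued uniformly over 23 months, and no loss to follow-up. With medians of 9 and 14 months, the looks fall at 26.9 and 36.3 months, close to the plan's 26 and 36. With both medians at 9 months they fall at 24.4 and 31.7, a gap of 7.3 months. If every signal were acted on, the expected difference in reporting time between the readings at HR 1 is (0.663 − 0.376) × 7.3 = 2.1 months. Both looks fall after accrual ends, so neither reading saves enrolment.

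**The case for a change.** The strongest case for a change is that the sentence before the rule ties the boundary to the overall type I error, which is 0.20, and the rule then refers back to that boundary. No 0.05 boundary, critical value or hazard-ratio cut-off is printed. The two readings give signal probabilities of 37–40% and 66–70% when the arms are equal, which is not a trivial difference. The wrong-side branch is also not negligible if the combination does far better than planned: its probability is 11–13% at a true hazard ratio of 0.50 and 41–44% at 0.40. A written rule should not rely on the reader to discard half of it, and the remedy is one sentence.

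What stands is that the wording is loose on both counts. What does not stand is that the rule is therefore undefined or wrong. To reach 80%, an analyst must replace a printed number with one that appears nowhere in the plan. A futility interval need not share the test level, and the 90% intervals for response and adverse events show that the plan does not tie its interval levels to the 20% test. In the wrong-side branch, the stated consequence and the following sentence settle the direction. The rule also only invites consideration, so a strongly positive trial could not be declared negative mechanically.

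**Conclusion.** The concern describes the wording correctly but does not call for a change. The natural reading is an O'Brien-Fleming shape evaluated at the printed 95%, with futility considered when the lower limit exceeds 0.64. At 80 of 105 events that means an observed hazard ratio above about 1.06 to 1.08. Spelling this out would give the same rule, the same decisions and the same operating characteristics: about 1% false signals at 0.64, no inflation of type I error, and power still at or above the stated 81%. The unnamed O'Brien-Fleming version moves the cut-off only from 1.057 to 1.075, and the critical value has to be computed at the actual information fraction in any case.

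Replacing 95% with 80% would change the rule, but it would exchange more early closures of an ineffective comparison for about six times as many false futility signals (5.8% against 1.0%, classic version) and slightly lower power. Nothing in the plan suggests that this was intended.

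The conclusion rests on reading the printed 95% as deliberate, on the rule remaining advisory, and on the usual large-sample approximation to the log-rank statistic. The 2.1-month figure further assumes exponential PFS, equal arms and use of the unprinted level.

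### Optional improvement: Boschloo's exact test would keep the 20% ceiling for the response-rate comparison and have equal or higher power than the planned Fisher test

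*Combined protocol and SAP*

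**What the plan says.** Section 9.3 makes progression-free survival the primary endpoint, with its own log-rank test at an overall two-sided 0.20 level. On response it states: "Response rate (RR) will be a secondary endpoint". The design claim is "With 138 patients there will be at least 80% power to detect an absolute difference of 20% in the objective response rates", illustrated by a difference "between 33% and 53% true response rates". The only test named for this comparison is a "two-group Fisher's exact test at an overall two-sided 20% significance level".

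Allocation is equal (Section 9.2: "Patients will be randomized with equal probability to treatment"), and Section 9.4 works with 69 per arm ("With at least 69 patients per treatment arm"). The figure of 138 is already net of the ineligibility allowance ("a maximum of 145 patients to allow for 5% ineligibility"). Section 6.1.1 further limits evaluability for response to patients with measurable disease at baseline who received at least one cycle and were re-evaluated, or who progressed before the end of cycle 1.

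**The concern.** Fisher's test conditions on the total number of responders. The attainable p-values are then coarse, and the true error rate usually falls below the nominal level. A two-sided 20% level is generous, so a test that runs well below it gives up some of the sensitivity that the level would allow.

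At stake is a modest amount of power on the first-listed secondary endpoint (Section 2.2.1). Borderline differences could be called non-significant at 20% when another exact test with the same guarantee would call them significant.

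**Working it through.** **Inputs.** 69 per arm (Sections 9.2 and 9.4); two-sided 0.20, Fisher's exact test, 33% v 53% (Section 9.3).

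**Fisher p-value.** For x and y responders with total t = x + y, let h(k) = C(69,k)·C(69,t−k)/C(138,t). The two-sided p-value is the sum of h(k) over all k with h(k) ≤ h(x).

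**Size and power.** With b the binomial probability, sum b(x; 69, p1)·b(y; 69, p2) over all of the 70 × 70 outcomes with Fisher p ≤ 0.20. Setting p1 = p2 gives the size; p1 = 0.33 and p2 = 0.53 gives the power.

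**The plan's own figure.** Power is 82.4%, so the claim of at least 80% reproduces. It also holds for the other 20-point differences checked (control rate 10% to 50%), where the lowest value is 82.2%.

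**Fisher's true size.**
- 69/69: 13.9% at a common rate of 33%, at most 14.8% at any rate.
- 68/70: at most 17.5%.
- 72/73 (all 145 patients): 16.3% at 33%, at most 18.4%.

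**Boschloo's test.** Take the Fisher p-value as the statistic. The Boschloo p-value is the largest probability, over all common response rates, of a Fisher p-value no greater than the one observed. Reject when it is ≤ 0.20. At 69/69 this amounts to rejecting when Fisher p ≤ 0.2328; the maximum size is 19.3% and the power 86.3%. Since 0.2328 exceeds 0.20, every table that Fisher rejects is also rejected.

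**Dependence on the split.** Power at 33% v 53%, control arm first; gains are taken before rounding.

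| Split | Fisher | Boschloo | Gain (points) |
|---|---|---|---|
| 69/69 | 82.4% | 86.3% | 3.9 |
| 70/68 | 83.2% | 84.0% | 0.8 |
| 68/70 | 85.8% | 86.0% | 0.3 |
| 72/73 | 86.5% | 86.6% | 0.1 |
| 65/65 (assumed) | 79.6% | 84.1% | 4.5 |
| 60/60 (assumed) | 78.9% | 80.6% | 1.8 |

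The last two rows assume further losses to evaluability; the documents give no expected number.

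**One table.** 23/69 v 31/69 (33% v 45%) gives Fisher p = 0.222 and Boschloo p = 0.174. With one more responder, 23/69 v 32/69, Fisher gives p = 0.164.

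**The case against.** The strongest reply is that nothing here is an error. The power is stated for Fisher's test itself, so its conservatism is already counted, and the claim is met. A nominal level is a ceiling, and the plan nowhere says that all 20% must be spent. Fisher's test is standard and valid, and conditioning on the number of responders is a defensible principle. Response is secondary: the sample size, the interim analysis and the early-reporting rule all rest on progression-free survival. All of this stands.

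The split also matters. The gain of about 4 points at 69/69 comes largely from exact equality of the arms. Stratified permuted blocks over three binary factors (eight strata), followed by ineligibility, do not guarantee equal analysed arms, and a shift of one patient from one arm to the other can cut the gain below one point.

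A further reply is that less conservative tests break the ceiling. That is true of the uncorrected chi-square test (size up to 24.2% at 69/69) and marginally of Fisher's mid-p (20.2%). It does not apply to Boschloo's test, which holds 20% by construction.

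A reader might infer more than the figures allow:
- That Fisher's test in general runs at about 14%. That is the 69/69 case only.
- That the plan forgoes power without any return. Fisher's test returns guaranteed error control and familiarity.
- That Fisher's test costs 12 patients, because it needs 75 per arm (150 in all) to reach 86.3%. With the same 138 patients split 68/70 it already has 85.8%.
- That response is a main reason for preferring the combination. The documents list it only as a secondary endpoint.

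**Conclusion.** The point holds as an optional improvement to a secondary analysis. The plan's level, test and power statement are all valid. Boschloo's test keeps the same ceiling of 20% at every response rate, rejects everything that Fisher's test rejects, and had no lower power in any split checked. At 33% v 53% the gain ranges from about 0.1 to 4.5 points.

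The gain is most useful if fewer patients than planned are evaluable for response. At an assumed 65 or 60 per arm, Fisher's power falls just below 80% while Boschloo's stays above it. The size of any such loss is an assumption.

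It would be tempting to raise the power claim to at least 85% after the change. The figures do not support that: Boschloo's power is 84.0% at 70/68 and 84.5% at 71/67, both with 138 patients.

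**What to change.** In Section 9.3, for the response-rate comparison, replace Fisher's exact test with Boschloo's exact unconditional test, stating that the two-sided Fisher p-value is the test statistic, at the same two-sided 20% level. Leave the power statement at 80%. Make the change before the response data are analysed by arm.

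The cost is one sentence. It needs no extra patients or data and does not affect the primary analysis. The test is available in standard software; the only downside is that readers know it less well than Fisher's.
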